### 8.3 Baseline Microbiological Assessments

Baseline pathogens will be summarized by genus and species, treatment group and overall for the microITT, microITT-2, emicroITT, and ME-TOC Analysis Sets. Selected pathogens will also be summarized by phenotypic susceptibility profile. In addition, for *Staphylococcus aureus* isolated at baseline, the PVL and MecA status (positive or negative) will be summarized. [Table 8](#) provides the definition for each pathogen susceptibility profile.

**Table 8. Definitions for Pathogen Susceptibility Profile**

Pathogen	Susceptibility Profile	Definition
Staphylococcus aureus	MSSA	Susceptible to ceftiofur
	MRSA	Resistant to ceftiofur
Streptococcus pneumoniae	PSSP	Susceptible to penicillin
	PISP	Intermediate susceptibility to penicillin
	PRSP	Resistant to penicillin
	Macrolide resistant	Resistant to azithromycin or erythromycin
	Quinolone resistant	Resistant to moxifloxacin
	Multidrug resistant	Resistant to 2 or more of the following classes of drugs: 
 
• Penicillins – oral penicillin
 
• Fluoroquinolones – moxifloxacin
 
• Cephalosporins – ceftriaxone
 
• Lincosamides – clindamycin
 
• Macrolides – azithromycin or erythromycin
 
• Tetracyclines – doxycycline
 
• Folate Pathway Inhibitors – trimethoprim/sulfamethoxazole
 

Haemophilus influenzae	B-lactamase positive	Zone diameter for ampicillin $\leq 18$ mm
	B-lactamase negative	Zone diameter for ampicillin $> 18$
Mycoplasma pneumoniae	Macrolide susceptible	Susceptible to azithromycin and erythromycin
	Macrolide resistant	Resistant to azithromycin or erythromycin
	Quinolone resistant	Resistant to moxifloxacin

Findings from the baseline Gram-stained respiratory specimens (ie, the best Gram stain reading) will be tabulated by treatment group and overall for subjects in the microITT, microITT-2, emicroITT and ME-TOC Analysis Sets. The number and percentage of subjects with a Gram-stained respiratory specimen that shows  $>25$  PMNs and  $<10$  SECs per LPF and  $\geq 10$  PMNs and  $<10$  SECs per LPF will be presented. In addition, summaries of PMNs and SECs and bacterial morphology for all Gram-stained respiratory specimens will be provided. Baseline for Gram stains is defined as the 24-hour period prior to the first dose of study drug and the 24-hour period after the first dose of study drug.

Baseline pathogens will be summarized by treatment group and overall, by genus and species, and diagnostic modality for the microITT, microITT-2, and ME-TOC Analysis Sets. The number and percentage of subjects with specimens tested, by testing modality, and the number and percentage of subjects with specimens positive for a pathogen and the specific pathogen (genus and species) will be presented. The number and percentage of subjects with monomicrobial or polymicrobial gram-positive or gram-negative pathogen infections, only atypical pathogens, a mixture of gram-positive and gram-negative pathogens, a mixture of gram-positive and atypical pathogens, a mixture of gram-negative and atypical pathogens or a mixture of gram-positive, gram-negative and atypical pathogens will be summarized by treatment group and overall for the microITT, microITT-2 and ME-TOC Analysis Sets.

The MIC distribution detailing the number and percentage of pathogens at the respective MIC values and the cumulative distribution will be presented for lefamulin and moxifloxacin by baseline pathogen, phenotype and study drug for both treatment groups combined and by treatment group for subjects in the microITT and ME-TOC Analysis Sets. Disk diffusion zone diameters for lefamulin and moxifloxacin will be summarized by baseline pathogen, phenotype, and study drug for both treatment groups combined and by treatment group for subjects in the microITT and ME-TOC Analysis Sets. Scatter plots of the MIC to lefamulin versus the disk diffusion zone diameter will be provided for *Streptococcus pneumoniae*, *Haemophilus influenzae*, *Staphylococcus aureus*, and *Moraxella catarrhalis*, as long as there are at least 10 pathogens in the lefamulin group.

The minimum inhibitory concentration 50 (MIC50), 90 (MIC90), and range of lefamulin and moxifloxacin for baseline pathogens and susceptibility (susceptible and resistant, based on MIC and zone diameter) of pathogens to lefamulin and moxifloxacin will be summarized by baseline pathogen for both treatment groups combined and by treatment group for subjects in the microITT and ME-TOC Analysis Sets. MIC50 and MIC90 will be provided only where there are at least 10 pathogens of a particular species; range will be provided for all pathogens.

Baseline pathogens are considered susceptible (S), intermediate (I), or resistant (R) to moxifloxacin and S or non-susceptible (NS) to lefamulin according to the criteria in [Table 9](#) and [Table 10](#).

**Table 9. Interpretive Criteria for Moxifloxacin for CABP Pathogens According to CLSI Guidelines**

Pathogen	Moxifloxacin MIC breakpoint a [µg/mL]			Moxifloxacin Disk Diffusion Zone Diameter a [mm]		
	S	I	R	S	I	R
Streptococcus pneumoniae	≤ 1	2	≥ 4	≥ 18	15-17	≤ 14
Staphylococcus spp.	≤ 0.5	1	≥ 2	≥ 24	21-23	≤ 20
Haemophilus influenzae	≤ 1	-	-	≥ 18	-	-
Moraxella catarrhalis	-	-	-	-	-	-
Legionella pneumophila	-	-	-	-	-	-
Mycoplasma pneumoniae b	≤ 0.25	-	≥ 0.5	-	-	-

S=susceptible, I=intermediate, R=resistant

a According to [CLSI M100-S25 \(2015\)](#)

b Breakpoints according to [CLSI M43-A \(2011\)](#)

**Table 10. Proposed Tentative Susceptibility Interpretive Criteria for Lefamulin for CABP Pathogens Based on *In Vitro* Data Determined According to CLSI Guidelines**

Pathogen	Lefamulin MIC breakpoint a [µg/mL]		Lefamulin Disk Diffusion Zone Diameter a [mm]	
	S	NS	S	NS
Streptococcus pneumoniae	≤ 1	> 1	≥ 19	< 19
Staphylococcus spp.	≤ 1	> 1	≥ 20	< 20
Haemophilus influenzae	≤ 2	> 2	≥ 20	< 20
Moraxella catarrhalis	≤ 1	> 1	≥ 20	< 20
Legionella pneumophila	≤ 1	> 1	- b	- b
Mycoplasma pneumoniae	≤ 1	> 1	- b	- b

S=susceptible, NS=non-susceptible

a The current absence of data on resistant isolates except for *S. aureus* precludes defining any category other than “susceptible.”

b No disk diffusion zone diameter criteria have been established for *M. pneumoniae* and *L. pneumophila*.

By-subject listings of pathogen MICs, susceptibilities, and disk diffusion zone diameters will also be provided.

## 8.4 Extent of Exposure and Study Drug Treatment Compliance

### 8.4.1 Duration of Study Drug Therapy

Duration of study drug treatment (placebo and/or active, as well as active only) will be summarized for the Safety and mITT Analysis Sets. Duration of study drug treatment is defined as the date of last dose – the date of first dose + 1. The number and percentage of subjects who received study drug for 1-2 days, ≥3-5 days, and 6-8 days as well as descriptive statistics of the number of days on study drug (n, mean, standard deviation, minimum, median, and maximum) will be presented by treatment group.

The proportion of subjects receiving all doses of study drug as inpatients, receiving all doses of study drug as outpatients and receiving doses of study drug as both inpatients and outpatients will be presented for the mITT Analysis Set.

### 8.4.2 Prior and Concomitant Medications

The World Health Organization (WHO) drug dictionary will be used to classify prior and concomitant medications, including antibacterial medications, by therapeutic class. A prior medication is defined as any medication taken prior to the date and time of the first dose of study drug (or date of randomization if no study drug was received). For non-antibacterials (for which only start and stop dates [not times] are collected), any medication taken on or after the date of first dose of study drug (or date of randomization if no study drug was received) will be considered concomitant; medications stop dates occurring prior to the date of first dose of study drug (or date of randomization if no study drug was received) will be considered prior medications. A concomitant medication is defined as any medication taken on or after the date and time of the first dose of study drug (or date of randomization if no study drug was received).

If the start date of a medication is missing, the medication will be assumed to be both prior and concomitant, unless the end date of the medication clearly indicates the medication was stopped prior to the first dose of study drug (or date of randomization if no study drug was received). If the start date is a partial date such that it cannot be determined if the medication is prior or concomitant, the medication will be assumed to be both prior and concomitant, unless the end date of the medication clearly indicates the medication stopped prior to the first dose of study drug (or date of randomization if no study drug was received).

For antibacterials, missing start and stop times will be set to 00:00 on the start and stop date of the antibiotic.

Prior systemic antibacterial medications and concomitant systemic antibacterial medications will be summarized by Anatomical Therapeutic Chemical (ATC) level 4 (or the next available level if level 4 is not available) and preferred term separately by treatment group for the ITT, mITT and CE-TOC Analysis Sets. Subjects receiving the same medication more than once will be counted only once for a particular ATC level and preferred term. Prior systemic antibacterial medications will be summarized based on receipt within 72 hours prior to randomization and receipt more than 72 hours prior to randomization.

Additional tables (ITT, mITT and CE-TOC Analysis Sets) will summarize the percent of subjects receiving any prior systemic antibacterial medication, the percent of subjects receiving an antibacterial medication in the 72 hours prior to randomization, the percent receiving the antibacterial for the current episode of CABP, the percent receiving a single dose of a short-acting oral or IV antibacterial for CABP (per the eCRF), the percent receiving more than 1 dose of a short-acting antibacterial for CABP or  $\geq 1$  dose of a long-acting antibacterial for CABP, the percentage of subjects receiving  $>48$  hours of prior systemic antibacterial therapy for the current episode of CABP enrolled as a treatment failure (ie, the exception to exclusion criterion 1), the percentage of subjects receiving a prior systemic antibacterial for an infection not related to CABP and the percentage of subjects receiving a prior systemic antibacterial for an “other” reason.

Prior and concomitant non-antibacterial medications will be presented in a by-subject listing and concomitant non-antibacterial medications will be summarized by ATC level 4 (or the next available level if level 4 is not available), preferred term and treatment group for the ITT Analysis Set. Subjects receiving the same medication more than once will be counted only once for a particular ATC level and preferred term.

The reasons for receipt of concomitant systemic antibacterial medications will be summarized by treatment group for the ITT, mITT and CE-TOC Analysis Sets. For concomitant systemic antibacterial medications, the number and percentage of subjects excluded from the CE Analysis Sets due to receipt of an antibacterial and not excluded from the CE Analysis Sets will be summarized. The reasons for receipt of the antibacterial will be provided for each category (excluded and not excluded from the CE Analysis Sets) and include current CABP prior to randomization, infection prior to randomization not related to CABP, concomitant infection unrelated to CABP, insufficient therapeutic effect of study drug (only for not excluded from the CE Analysis Sets), treatment-limiting AE resulting in study drug discontinuation (only for not excluded from the CE Analysis Sets), and “other.”

### 8.4.3 Study Drug Treatment Compliance

Each subject's compliance with study drug treatment will be calculated based on the number of doses the subject would have been expected to receive based on the number of treatment days (ie, the date of the first and last dose of study drug). Treatment compliance is defined as the number of doses actually received divided by the number of doses expected for the time period between the dates of the first and last doses of study drug ( $\times 100$ ). Subjects are expected to receive 7 days of study drug (5 days of active lefamulin plus 2 days of placebo) or moxifloxacin (7 days of active moxifloxacin). Descriptive statistics (number of subjects, mean, standard deviation, minimum, median, and maximum) will be presented for the ITT, microITT, CE-EOT and CE-TOC Analysis Sets.

## 8.5 Efficacy Analyses

For all efficacy analyses, subjects will be analyzed in the group to which they were randomized. By definition, subjects who receive the wrong study drug are not included in the CE and ME Analysis Sets. Unless otherwise stated, subjects who are randomized to the wrong geographic region, prior antibiotic, or PORT risk class stratum will be analyzed in the stratum to which they were randomized.

### 8.5.1 Primary Efficacy Analysis

The primary efficacy outcome is the percentage of subjects with an ECR of responder at  $96 \pm 24$  hours after the first dose of study drug in the ITT Analysis Set. Each subject will be programmatically categorized as a responder, non-responder, or indeterminate based on data on the eCRF. Subjects with missing data or who are lost to follow up are defined as indeterminate for the primary analysis and are included in the denominator for the calculation of the response rate. Thus, subjects with an indeterminate outcome are considered non-responders for the primary analysis. The number and percentage of subjects in each treatment group in each response category (and combined non-responder/indeterminate) will be reported.

The null and alternative hypotheses are:

$$H_0: P_1 - P_2 \leq -\Delta$$

$$H_1: P_1 - P_2 > -\Delta$$

Where  $P_1$  = the primary efficacy outcome rate in the lefamulin group

$P_2$  = the primary efficacy outcome rate in the moxifloxacin group

$\Delta$  = the non-inferiority margin

The NI hypothesis test is a 1-sided hypothesis test performed at the 2.5% level of significance. This is based on the lower limit of the 2-sided 95% confidence interval (CI) for the observed difference in the early clinical response rate (lefamulin group minus the moxifloxacin group). The CI will be calculated using an unadjusted continuity corrected Z-test. If the lower limit of the 95% CI for the difference in responder rates in the ITT Analysis Set is greater than -10%, the null hypothesis will be rejected and the NI of lefamulin to moxifloxacin will be concluded.

The reasons for an ECR of non-responder and indeterminate will be summarized by treatment group for all subjects who are a non-responder or indeterminate at  $96 \pm 24$  hours after the first

dose of study drug. Reasons for non-responder are: did not show improvement in at least 2 of the cardinal symptoms of CABP, worsening of at least 1 symptom of CABP, received a concomitant antibacterial and died from any cause. Reasons for indeterminate are: no assessment of symptoms and did not have at least 2 cardinal symptoms at baseline.

### 8.5.2 Additional Analyses of the Primary Efficacy Outcome

Early Clinical Response will be assessed separately across the randomization stratification factors (from the IRT) of geographic regions (US vs. ex-US), prior antibiotic use vs. none, and PORT risk class (II vs. III/IV). For each geographic region, prior antibiotic use, and PORT risk class stratum a 2-sided 95% CI for the observed difference in ECR responder rates will be calculated for the ITT Analysis Set.

Sensitivity analyses of early clinical response include:

- An analysis adjusted for the stratification factors of geographic region, prior antibiotic use and PORT risk class stratum (based on the randomization stratum the subject was actually randomized to). A 95% CI using the method proposed with stratification by Miettinen and Nurminen will be computed for the difference in the ECR responder rates between lefamulin and moxifloxacin. Cochran-Mantel-Haenszel weights will be used for the stratum weights in the calculation of the CI.
- An analysis adjusted for the stratification factors of geographic region, prior antibiotic use, and PORT risk class stratum based on the randomization stratum the subject correctly belongs to. A 95% CI using the method proposed with stratification by Miettinen and Nurminen will be computed for the difference in the ECR responder rates between lefamulin and moxifloxacin. Cochran-Mantel-Haenszel weights will be used for the stratum weights in the calculation of the CI.
- All subjects with missing data at  $96 \pm 24$  hours after the first dose of study drug or with less than 2 symptoms at baseline (ie, indeterminates) as ECR responders (these subjects are considered ECR non-responders in the primary analysis). An unadjusted 95% CI will be computed using a continuity corrected Z-test for the difference in the ECR responder rates between lefamulin and moxifloxacin.
- Subjects who are non-responders and receive less than 48 hours total duration of study drug will be reclassified as indeterminates and the number and percentage of subjects in each treatment group in each response category will be reported. Subjects who died prior to receipt of at least 48 hours total duration of study drug will remain classified as a non-responder. An unadjusted 95% CI will be computed using a continuity corrected Z-test for the difference in the ECR responder rates between lefamulin and moxifloxacin.

Subgroup analyses of the primary efficacy outcome, including treatment differences and 95% CIs (computed using a continuity corrected Z-test), will also be conducted for descriptive purposes. These include but are not limited to PORT Risk Class per the eCRF (II, III, IV), prior antibiotic use in the 72 hours before randomization per the eCRF (use, no use), SIRS (yes, no), ATS (yes, no), CURB-65, gender, age group (<65, 65-74,  $\geq 75$  years), renal impairment category and bacteremic subjects. Exploratory analyses in other subgroups may also be conducted. A

Forest plot of the treatment difference in ECR responder rate and CI by the stratification factors and subgroups will also be provided.

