Additional analyses of the primary efficacy outcome will be conducted. ECR will be assessed separately across the geographic regions, prior antibiotic use, and PORT risk class strata. For each geographic region, prior antibiotic use, and PORT risk class stratum, a 2-sided 95% CI for the observed difference in ECR responder rates will be calculated for the ITT Analysis Set. Sensitivity analyses of ECR include determination of a stratified 95% CI (adjusted for the randomization stratification factors) and considering all subjects with missing data (i.e., Indeterminates) at  $96 \pm 24$  hours after the first dose of study drug as responders for ECR (these subjects are considered non-responders in the primary analysis). For the second sensitivity analysis, an unstratified 95% CI will be computed for the difference in the responder rates between lefamulin and moxifloxacin. Subgroup analyses of the primary efficacy outcome will also be conducted for descriptive purposes and will be detailed in the SAP. For both ECR and IACR, additional analyses will be conducted whereby failures will be reclassified as Indeterminate if they received less than 48 hours of study medication.

For the EMA primary analysis (secondary analysis for the FDA), the number and percentage of subjects in each treatment group with an IACR of Success, Failure and Indeterminate (by definition Indeterminates are not included in the CE-TOC Analysis Set) at TOC will be reported in the mITT and CE-TOC Analysis. Subjects who have an IACR of Failure at EOT will be considered to have an IACR of Failure at TOC. The primary analysis for the EMA will utilize 2-sided stratified (for the randomization stratification factors) 95% CIs calculated using the method of Miettinen-Nurminen. If the lower limit of the 95% CI for the difference in success rates in both the mITT and CE-TOC Analysis Sets is greater than -10%, the NI of lefamulin to moxifloxacin will be concluded. Two-sided unstratified 95% CIs will be calculated for the difference in success rates at TOC in the mITT and CE-TOC Analysis Sets (FDA secondary outcome).

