#### 9.8 Handling of Missing Data

For the primary outcome measure (FDA), if any data field needed to determine ECR is missing, the subject will be assigned a response of Indeterminate. Imputations for the missing times will be provided in the SAP. For analyses of the primary outcome, subjects with an indeterminate response are included in the denominator, and thus are considered Non-responders. A sensitivity analysis of the primary outcome will be conducted in which subjects with an indeterminate response are considered Responders.

For the outcome measure of IACR at EOT, TOC and LFU, missing data are considered as a response of Indeterminate. For analysis in the ITT, mITT and microITT Analysis Sets, indeterminate outcomes are included in the denominator and are thus, considered clinical Failures. By definition, subjects with an IACR of Indeterminate are excluded from the CE-EOT, CE-TOC, CE-LFU, ME-EOT, ME-TOC, and ME-LFU Analysis Sets.

A missing microbiological response is considered a presumed response based on the IACR. For analysis in the microITT Analysis Set, indeterminate outcomes are included in the denominator and are thus, considered microbiological failures. By definition, subjects with an IACR of Indeterminate are excluded from the ME Analysis Sets.

Handling of missing data for other efficacy and safety outcomes will be presented in the SAP.

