- If no assessment was conducted in person in the 60 to <72 hour window, use the latest assessment of symptoms conducted via a telephone call occurring 60 to <72 hours after the first dose of study drug

Subjects with missing data such that a response cannot be determined will be considered an indeterminate response. Subjects who are randomized and not treated or did not have at least 2 symptoms of CABP at baseline will also be considered to have an indeterminate response. Since the analysis of the primary outcome is based on the ITT Analysis Set, subjects with an indeterminate response are essentially considered non-responders. For the ITT Analysis Set, the percentage of ITT subjects considered responders for ECR is defined using the following formula (where the denominator is comprised of the total number of subjects in the ITT Analysis Set):

$$\frac{\text{Number of subjects who are a responder}}{(\text{Number of subjects who are a responder} + \text{Number of subjects who are a non-responder} + \text{Number of indeterminate subjects})} \times 100\%$$

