## 7.6 Handling of Missing Data

For ECR, missing data will be handled as follows:

- If any component of ECR is missing in the time frame detailed in Section 6.1 (unless the subject dies or is deemed a failure prior to this time point), or if the subject does not have at least 2 symptoms of CABP at baseline, ECR will be defined as an indeterminate.
- If the time of a post-baseline assessment of CABP symptoms obtained in the window for determination of ECR is missing but the date of the ECR assessment is known, the time will be imputed to noon on the date of the CABP symptom assessment. If the time of assessment of CABP symptoms obtained on or prior to the date of the first dose of study drug is missing, the time will be imputed to 00:00.
- Missing start and stop times of antibiotics will be set to 00:00 on the start and stop date of the antibiotic.
- For the analysis of ECR in the ITT Analysis Set, where ECR may be missing (indeterminate), all subjects in the ITT Analysis Set will be included in the denominator. Thus, subjects with an indeterminate response are essentially considered as a failure.

For IACR, missing data will be handled as follows:

- A missing IACR at the EOT Visit will be considered indeterminate at the EOT Visit.
- A missing IACR at the TOC Visit will be considered indeterminate unless the IACR at the EOT Visit is failure. An IACR of failure at the EOT Visit will be carried forward to the TOC Visit.
- A missing IACR at the LFU Visit will be considered indeterminate unless the IACR at the TOC Visit is failure. An IACR of failure at the TOC Visit will be carried forward to the LFU Visit.
- For the analysis of IACR at the EOT, TOC and LFU Visits in the mITT, microITT, microITT-2 and emicroITT Analysis Sets, where Clinical Response may be missing (indeterminate), all subjects who meet the analysis set criteria will be included in the denominator.
- For the analysis of IACR at the EOT, TOC and LFU Visits in the CE and ME Analysis Sets, subjects with a missing (indeterminate) IACR will not be included in the analyses, since by definition, subjects in the CE or ME Analysis Sets cannot have a missing IACR.

For microbiological response, missing data will be handled as follows:

- If a followup specimen for culture was not obtained, microbiological response at the EOT Visit will be determined based on the IACR at the EOT Visit.

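### The under-48-hour ECR sensitivity analysis moves subjects between two categories that both count as non-response, so its confidence interval always equals the primary one

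*SAP*

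**What the plan says.** SAP 8.5.2 lists four sensitivity analyses of ECR. The fourth reads: "Subjects who are non-responders and receive less than 48 hours total duration of study drug will be reclassified as indeterminates". It adds an exception: "Subjects who died prior to receipt of at least 48 hours total duration of study drug will remain classified as a non-responder". Two outputs are requested: counts and percentages by response category, and a CI, specified as "An unadjusted 95% CI will be computed using a continuity corrected Z-test for the difference in the ECR responder rates between lefamulin and moxifloxacin".

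Three other places in the SAP fix how indeterminates are scored:

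- SAP 6.1 defines the ITT responder rate as responders over the sum of responders, non-responders and indeterminates, and notes that "subjects with an indeterminate response are essentially considered non-responders".
- SAP 7.6 puts every ITT subject in the denominator for ECR in that set: "Thus, subjects with an indeterminate response are essentially considered as a failure".
- SAP 8.5.1, which defines the primary CI by the same unadjusted continuity-corrected method, says: "Thus, subjects with an indeterminate outcome are considered non-responders for the primary analysis".

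The analysis originates in Protocol 9.6.1, where, for both ECR and the investigator's assessment (IACR), "failures will be reclassified as Indeterminate if they received less than 48 hours of study medication". The protocol gives no scoring rule for the reclassified subjects and, for IACR, names no analysis set. Protocol 9.8 says of IACR in the ITT, mITT and microITT sets that "indeterminate outcomes are included in the denominator and are thus, considered clinical Failures".

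**The concern.** A sensitivity analysis is informative only if it could have given a different answer. This one relabels some zero-scored subjects as another kind of zero-scored subject and then recomputes a rate that depends only on the responder count and the ITT total. Reported as planned, its CI would agree exactly with the primary result, and a reader could take that as evidence that short exposure does not drive the treatment difference. That question would not have been examined.

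The third bullet of the same section shows the contrast. It states a new scoring rule, counting indeterminates as responders, so its CI can move. The fourth bullet states none.

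**Working it through.** **Inputs from the documents.** 369 subjects per arm, 79% anticipated response, 10% margin, one-sided alpha 0.025, and a continuity-corrected Z-test with unpooled variance (SAP 7.1). The rate formula is in SAP 6.1, the denominator rule in SAP 7.6 and the CI method in SAP 8.5.1 and 8.5.2.

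**The plan's own figure.** This confirms the form of the test.

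- SE = sqrt(2 × 0.79 × 0.21 / 369) = 0.02999
- Continuity term = 0.5 × (1/369 + 1/369) = 0.00271
- Power = Φ((0.10 − 0.00271)/0.02999 − 1.96) = 90.05%

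The stated 90% is reproduced.

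**The identity.** For each arm, let R, NR and I be the numbers of responders, non-responders and indeterminates. The rate is p = R/(R + NR + I). Move k subjects from NR to I:

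p′ = R / (R + (NR − k) + (I + k)) = R/(R + NR + I) = p

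The CI is d ± [1.96 × sqrt(p1q1/n1 + p2q2/n2) + 0.5 × (1/n1 + 1/n2)], with d = p1 − p2 and q = 1 − p. It depends only on p1, p2, n1 and n2, and none of these changes. The death exception only reduces k, so it cannot matter either.

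**Numerical check.** The documents give no counts, so these are assumed: R/NR/I = 285/74/10 (lefamulin) and 292/67/10 (moxifloxacin).

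- Primary: d = 0.7724 − 0.7913 = −1.90%; SE = 0.0304; half-width = 1.96 × 0.0304 + 0.0027 = 0.0623; CI −8.13% to 4.33%.
- Planned fourth analysis with 12 and 6 reclassified:

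| Category | Lefamulin before → after | Moxifloxacin before → after |
|---|---|---|
| Non-responder | 20.1% → 16.8% | 18.2% → 16.5% |
| Indeterminate | 2.7% → 6.0% | 2.7% → 4.3% |
| Responder | 285/369, unchanged | 292/369, unchanged |

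The CI remains −8.13% to 4.33%. Trying every possible pair (0 to 74 in one arm, 0 to 67 in the other, so 75 × 68 = 5100) gives that single CI. Holding back 2 and 1 deaths as non-responders also leaves it unchanged.

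**What a CI able to move would show.** Take the same counts and exclude everyone with under 48 hours of drug. Further assumptions: 3 responders per arm also had short exposure, there were no early deaths, and none of the 10 indeterminates per arm was untreated or had short exposure, so all of them stay in.

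| Short-exposure non-responders (lefamulin, moxifloxacin) | Rates | Difference (95% CI) |
|---|---|---|
| 12, 6 | 282/354 vs 289/360 | −0.62% (−6.77 to 5.54) |
| 20, 5 | 282/346 vs 289/361 | +1.45% (−4.64 to 7.54) |
| 6, 12 | 282/360 vs 289/354 | −3.31% (−9.45 to 2.84) |
| 5, 15 | 282/361 vs 289/351 | −4.22% (−10.34 to 1.90) |

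**Why the rule must be fixed beforehand.** Take 282/369 vs 292/369 with 5 and 15 non-responders reclassified. The primary lower limit is −8.98%. It becomes −11.13% if the reclassified subjects leave the denominator, and −11.40% if they are scored as responders. Two rules that the SAP does not state would each fall on the other side of −10%.

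**The case against.** The algebra is hard to dispute. The best counter-argument is that the bullet is underspecified rather than degenerate. Much of the SAP's wording on scoring indeterminates as non-responders is tied to the primary analysis, and the fourth bullet is not the primary analysis. A death exception would be pointless for a CI unless indeterminates were to be scored differently, so a scoring sentence may have been left out. That may well be what happened. However, SAP 7.6 applies its denominator rule to ECR in the ITT set generally, and no text supports another rule for this bullet. If a sentence was omitted, it still has to be added.

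A second argument is proportion. No decision depends on this CI, the other three sensitivity analyses are sound, and Protocol 9.6.1 asks for the reclassification without asking for a CI. All of this is true, and it limits the point to a correction that should be made rather than a threat to the trial's conclusion.

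Third, for IACR, SAP 5.6 criterion 4 already removes subjects with under 48 hours of drug from the CE sets, except those who died before 48 hours. The FDA SAP's IACR section does not carry the reclassification over, and the EMA addendum is not among the documents reviewed. The IACR remark is therefore conditional. The CE rule concerns a different analysis set and does nothing for the ECR bullet.

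Finally, excluding short-exposure subjects is a different analysis from the planned one and departs from ITT. Keeping early deaths while dropping others also means the exclusion is not wholly independent of outcome. Both are fair, and they are why that option can only be supportive.

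**Conclusion.** The concern holds. Under the SAP's own definitions, the fourth ECR sensitivity CI equals the primary CI for any data. This is an identity and does not depend on the assumed counts, which serve only as illustration. It rests on one reading: that the ITT denominator rule in SAP 7.6 governs this bullet, which is the only rule the text supplies.

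The effect is limited to this CI and the responder rates behind it. The primary test, the 10% margin and the non-inferiority decision stand. The shift between the non-responder and indeterminate rows is real and worth reporting as description. If the IACR version in Protocol 9.6.1 were run in mITT, the same identity would apply.

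**What to change.** Amend the fourth bullet of SAP 8.5.2 before database lock, in one of two ways:

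- **(a) Make the CI able to differ.** Compute it after removing from both numerator and denominator every subject with under 48 hours of study drug, whatever the response and including those randomized but never treated. Subjects who died before 48 hours stay in as non-responders. Label the result supportive.
- **(b) Drop the CI.** Keep the response-category table as a descriptive display and delete the sentence asking for the interval.

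If the IACR version in Protocol 9.6.1 is retained, name its analysis set and apply the same choice in mITT.

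The cost is one sentence and at most one re-specified table, with no new data. The drawback of (a) is that it is a post-randomization exclusion and so not an ITT comparison. Option (b) loses nothing, since the deleted CI repeats the primary result.
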